Part 2 extension: Assuming there are no safety signals from the day 7 review following dosing children with 30 and 40 mg/kg of product, and prior to the last study visit of the original protocol described above (September 2022 to June 2024), study participants who remain enrolled in the part 2 efficacy study will be invited to participate in a 12-month extension of the study. A separate written consent process will take place. Enrolled children will continue in the same study groups as in part 2: 1 dose L9LS, 2 doses L9LS, or placebo. A dose (of L9LS or placebo) will be given at the start of the extension and again after six months. Those receiving L9LS will receive a dose between 20 and 40 mg/kg, still in a double-blinded fashion. The monthly visit and sample collection schedule will mirror that in part 2.

Objectives:

Primary Objectives:

Part 1:

1. Safety: To evaluate the safety and tolerability of L9LS administered at doses of 5 mg/kg, 10 mg/kg, and 20 mg/kg by SC administration to healthy Kenyan children.

Part 1b:

1. Safety: To evaluate the safety and tolerability of L9LS administered at doses of 30 mg/kg and 40 mg/kg by SC administration to healthy Kenyan children

Part 2:

1. Safety: To evaluate the safety and tolerability of L9LS administered at doses of 10-20 mg/kg by SC administration to healthy Kenyan children.

2. Efficacy: To assess the efficacy of two doses of L9LS at a concentration of 10-20 mg/kg, administered SC to participants aged 5-59 months of age against first/only Pf malaria infection diagnosed by blood smear microscopy (irrespective of fever) over 12 months compared to placebo.

Secondary Objectives:

- 1. To assess the efficacy of one dose of L9LS at 10-20 mg/kg against first/only Pf malaria infection diagnosed by blood smear microscopy over 3 and 6 months compared to placebo.
- 2. To assess the efficacy of one dose of L9LS at 10-20 mg/kg against first/only Pf malaria infection diagnosed by blood smear microscopy over 12 months compared to placebo.
- 3. To evaluate the efficacy of L9LS at 10-20 mg/kg against first/only Pf malaria infection as detected by PCR over 3, 6 and 12 months compared to placebo.
- 4. To assess protection of L9LS at 10-20 mg/kg against clinical malaria (first/only and all episodes) at 3, 6 and 12 months compared to a placebo.
- 5. To assess the primary objective and secondary objectives 1-4 among children 5-17 months of age.

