The CDC has collaborated with KEMRI in western Kenya to evaluate tools for malaria transmission and burden reduction for over 40 years. The collaboration has a highly experienced clinical trials unit that includes two pediatricians, immunologists, medical officers, pharmacists, clinical officers, nurses, quality control and regulatory officers. This group has been involved in phase 2, 3, and 4 trials of RTS,S/AS01 and conducted the largest phase 2 trial of the PfSPZ Vaccine in 5- to 12-month-old infants as well as a number of pharmaceutical clinical trials. The clinical trials unit is based in Siaya County Referral Hospital, the largest hospital in Siaya County, western Kenya. Here, malaria transmission is perennial with seasonal peaks following the long and short rains in June/July and November/December, respectively. Clinical malaria incidence (any parasite density by microscopy in a child who reports fever within the previous 24 hours) among children aged 5 to 17 months was 3.06 cases per year in 2019–2020. In the recent PfSPZ Vaccine trial among infants 5-12 months of age at the time of first vaccination (with a 3-dose series over 5 months), 66.7% of participants in the placebo arm had at least one Pf infection based on microscopy within 6 months after the last dose; in another trial among 5- to 17-month-olds at the time of first vaccination (with a 3-dose series over 3 months), 46.8% had at least one clinical malaria episode (parasitemia >0 parasites/µL and fever/history of fever within 24 hours) within 6 months after the last dose. Currently, the RTS,S/AS01 malaria vaccine is being rolled out by the Kenya Expanded Programme on Immunization in select sub-counties in western Kenya; the RTS,S/AS01 vaccine is not being implemented in Alego-Usonga sub-county (where the clinical research site is located). The current Malaria Vaccine Pilot Evaluation is scheduled to run until May 2023, so the earliest that RTS,S/AS01 vaccinations would be offered in Karemo, where the study site hospital is, would be June 2023. In part 2, staff will also recruit and follow up patients at Kogelo Dispensary, a satellite clinic referring patients to Siaya County Referral Hospital.

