9.2.2 Sample Size Considerations for the Efficacy Study

Table 6 shows initial sample size estimations powered to detect a 70% vaccine efficacy (1 – [proportion infected in L9LS/proportion infection in control]) at 12 months comparing L9LS at 10-20 mg/kg to placebo. Sample size calculations were done assuming the endpoint of any Pf infection will be calculated using a proportional analysis, 80% or 90% power, an alpha of 0.05, and that either 30%, 35%, or 40% of children in the placebo group are infected at 6 months and that 40% or 45% are infected at 12 months. (Time-to-event analyses typically require smaller sample sizes.) The primary endpoint will be at 12 months and will combine both MAb age groups who received two doses of L9LS and compare those subjects to the overall placebo group, i.e., we will assess MAb efficacy among children 5–59 months. However, the trial sample size is based on the secondary endpoint of 12-month MAb efficacy with two doses among the younger age group (5–17 months) versus the 5–17-month-old subjects in the placebo group, as these will require larger sample sizes than the primary endpoint. Factoring in 25% loss to followup over 12 months, and a doubling of the sample size in each intervention arm to allow for comparison of L9LS with a second dose (at 6 months) to placebo and comparison of L9LS without a second dose to placebo would require 108 children in each L9LS group and 54 children in the placebo arm, assuming 35% infected in the placebo group at 6 months.

Abbreviated Title: Anti-malaria MAb in Kenyan children

Version 6.0 Date: 2 Apr 2024

Table 6. Sample size calculations based on secondary 12-month endpoint, to achieve 80% power to detect efficacy of 70% at 6 months and 60% at 12 months, assuming 35% of the control group are infected by 6 months and 45% by 12 months.

| Arm | Assumed proportion infected in control group by 6 mos | mAb Efficacy at 6 months | Power | Number needed at 6 months | | Assumed % infected in control group by 12 mos | mAb Efficacy at 12 months | Number needed at 12 months | Number needed to enroll | Number with 20% LTFU* |
|------------------------------|---|-----------------------------------|----------|---------------------------------|-----|---|------------------------------------|-------------------------------------|-------------------------------|-----------------------|
| mAb 5-17 mos + Dose 2 | 0.30 | 70% | 80% | 50 | 120 | 0.40 | 60% | 52 | 104 | 130 |

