9.5.1 General Approach

In general, descriptive statistics will be tabulated by treatment arm for endpoints of interest. This will include point estimates (mean, geometric mean, median, or proportions) and their respective 95% confidence intervals. Formal comparisons will use standard methods, contingency tables for categorical variables, t-tests for comparing means if data follow a normal distribution or geometric means if data after log transformation follow a normal distribution, or nonparametric analogs for comparing medians. Unless specified in the subsequent sections, comparisons will be two-sided with type I error rate of 0.05.

Missing data will be considered as "missing completely at random" provided the amount of missing data is modest (e.g., <10%). We will examine the "missing completely at random"

assumption if the amount of missing data is more than 10%. If the assumption does not hold, missing data will be handled under the "missing at random" assumption (that is, missingness depends only on observed variables) via methods such as multiple imputation and inverse propensity weighting. To handle the possibility of "missing not at random," a sensitivity analysis will be performed by imputing missing binary observations with the observed proportion in the opposite arm. A secondary sensitivity analysis will be considered by imputing missing binary observations as failures.

Randomization: In the efficacy study, participants will be stratified by age (5-17 months versus 18-59 months) and then each age group will be randomized **2:1** to the L9LS arm and the placebo arm. The total number of participants will be 108 in each arm. In the dose-escalation study, participants in each age group, starting with 5-10 years, followed by 5-59 months, will be recruited and randomized 3:1 to receive L9LS at the dose of 5 mg/kg or placebo; if no safety concerns arise, randomization into the L9LS at the dose of 10 mg/kg or placebo, and finally 20 mg/kg or placebo, ensues in the same manner. To limit the number of dropouts before L9LS administration, randomization and L9LS administration will occur as close in time as possible.

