Finally, all clinical malaria episodes will be included in exploratory analyses. All person-time during the trial, including the time after the initial positive evaluation for Pf infection or clinical malaria, will be included in these analyses. This approach will use a counting process which is an extension of the Cox proportional hazards model to incorporate multiple events. 35 The 14 days following treatment with artemether-lumefantrine will be removed from these analysis. In these models the number of prior events will be included as a covariate in order to ensure that the conditional independence assumption of the counting process is still met since a previous infection may confer some future protection. 36

Although the trial will not be weight-stratified, given that we have age stratification, we anticipate that participants will cover the dose range from 10 mg/kg to 20 mg/kg in the efficacy analyses. In addition to the above efficacy analyses that compare each dose arm with the placebo arm, an exploratory analysis will be additionally conducted to assess how dosage, in terms of mg of L9LS per kg of subject body weight, affects the protective efficacy.

Making these data available in a timely manner will add to the evidence base needed to plan a potential phase 3 trial of L9LS in settings with seasonal malaria transmission.

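### The only all-episodes comparison between arms is labelled exploratory and adjusts for prior episode count, so it does not give the total effect that secondary objective 4 asks for

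*Combined protocol and SAP*

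**What the plan says.** The abstract (section 1.1) and the objectives table (section 3) make it a secondary objective to assess protection "against clinical malaria (first/only and all episodes) at 3, 6 and 12 months compared to a placebo". Objective 5 extends this to the younger stratum ("To assess the primary objective and secondary objectives 1-4 among children 5-17 months of age"), and objective 6 does the same for 18-59 months.

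Section 9.5.4 has two non-exploratory efficacy methods: time to first infection (log-rank and Cox, allowing for interval censoring) and the proportion infected from one minus Kaplan-Meier. Both stop at the first event. The section then says that "all clinical malaria episodes will be included in exploratory analyses", using a counting-process extension of the Cox model with the 14 days after artemether-lumefantrine removed. It adds: "In these models the number of prior events will be included as a covariate". The reason given is conditional independence, "since a previous infection may confer some future protection". It specifies no version without that covariate and no variance clustered on the child.

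Section 9.5.1 provides for descriptive estimates by arm ("This will include point estimates (mean, geometric mean, median, or proportions) and their respective 95% confidence intervals") and for generic two-arm comparisons, without naming episode counts. Section 9.5 says that a detailed SAP, which supersedes the protocol, will be written before unblinding.

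**The concern.** There are two problems. First, the labels disagree: half of a secondary objective has only an exploratory analysis.

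Second, the number of prior episodes is an outcome that arises after dosing. Adjusting for it compares an L9LS child and a placebo child who have had the same number of episodes so far, and those two children are not exchangeable. If exposure varies between children, the L9LS child has reached that count despite protection and so tends to be the more exposed one. Efficacy is then pulled toward no effect. If earlier episodes instead protect against later ones, as the protocol supposes, the count lies on the path from assignment to later episodes. Adjusting then removes the part of the total effect that arises because placebo children acquire more of this protection, and efficacy comes out above the total effect.

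At stake is the reported efficacy for the all-episodes half of objective 4, most of all in the 5-17 month analysis, where episodes may be frequent.

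**Working it through.** **The plan's own figure.** No figure is stated for the all-episodes analysis. The sizing figure nearest to it, 43 per group in Table 6 (45% v 18%, 80% power, two-sided 0.05), reproduces: (1.960 + 0.842)² × (0.45×0.55 + 0.18×0.82) / 0.27² = 7.85 × 0.3951 / 0.0729 = 42.5, so 43. Then 43/0.8 = 53.75, so 54. It concerns a first infection and this point does not change it.

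**Inputs from the documents**
- Placebo risk: section 9.2.2 assumes that "40% or 45% are infected at 12 months". At equal exposure, 45% gives −ln(0.55) = 0.60 per year.
- Background rate: the study-site text in section 4.1.1 says that clinical malaria incidence "among children aged 5 to 17 months was 3.06 cases per year".
- Efficacy at 12 months: 60% (Table 6), so a hazard ratio of 0.40.
- At-risk rule: 14 days removed, applied here after each simulated episode.

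**Assumed, because the documents give no value**
- Gamma frailty variance v, with mean 1, to represent uneven exposure: 0 to 1.
- Hazard multiplier per prior episode, to represent acquired protection: 1, 0.9 or 0.8.

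**Mechanism.** Ignoring the 14-day gaps, a child with k episodes after cumulative hazard H has expected frailty (1/v + k)/(1/v + H). At equal k, the hazard ratio between arms is therefore 0.40 × (1/v + H0)/(1/v + H1), where H1 = 0.4 × H0.
- 3.06/year, v = 0.5, end of year: 0.40 × (2 + 3.06)/(2 + 1.224) = 0.628, or 37% efficacy at equal count.
- 0.6/year, v = 1, end of year: 0.40 × (1 + 0.6)/(1 + 0.24) = 0.516, or 48%.

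At the start of follow-up the figure is 60% in both cases. An average over the year must lie between the two values.

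**Simulation.** Hazard models: arm-only, λ0(t)·exp(β·arm); planned, λ0(t)·exp(β·arm + γ·prior count). Follow-up runs from about day 7 to day 364. The 12-month figures use 40,000 children per arm in four runs (Monte Carlo standard error at most 0.5 points). The 3- and 6-month figures carry noise of about 1 point. Efficacy, arm-only v planned:

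| Scenario | 3 months | 6 months | 12 months |
|---|---|---|---|
| 0.6/year, v = 0 | – | – | 60 v 60% |
| 0.6/year, v = 0.5 | – | – | 59 v 57% |
| 0.6/year, v = 1 | 59 v 58% | 60 v 58% | 59 v 55% |
| 3.06/year, v = 0 | – | – | 60 v 60% |
| 3.06/year, v = 0.5 | 59 v 57% | 59 v 54% | 59 v 50% |
| 3.06/year, v = 1 | 58 v 54% | 58 v 50% | 58 v 45% |
| 3.06/year, v = 0, ×0.9 per episode | – | – | 57 v 60% |
| 3.06/year, v = 0, ×0.8 per episode | – | – | 55 v 60% |
| 3.06/year, v = 0.25, ×0.8 per episode | – | – | 54 v 54% |

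A separate run put the 0.6/year, v = 1 result at 12 months at 59 v 54%, so the gap there is 4 to 5 points. In a further independent set of runs at 3.06/year, the arm-only model matched the crude episode rate ratio in every scenario (for example 0.424, or 58%, at v = 1).

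The fitted hazard ratio per prior episode was 1.00 both with no frailty and no acquired protection, and with v = 0.25 and ×0.8. The fitted coefficient therefore cannot show which mechanism is at work.

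**The case against.** The strongest reply is that the planned coefficient is a legitimate conditional effect, with a stated reason and cited methods. Under the protocol's own premise (acquired protection, equal exposure) it returns the 60% direct effect, while the arm-only model gives 57% or 55%. This stands to the extent that the model targets a different quantity and is not mistaken. But objective 4 asks about protection compared with placebo, which is most naturally the total effect of assignment. Dependence within a child can be handled by clustered variance without changing the target.

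The larger gaps rest on an assumed frailty variance and on a 2019-2020 background rate. In the trial every child first receives dihydroartemisinin-piperaquine, and every positive smear is treated regardless of symptoms (section 2.2.2.3), which could lower the rate. The 0.6/year comes from an any-infection assumption, not clinical episodes. The simulation also removes time only after simulated episodes, whereas the plan removes it after any artemether-lumefantrine treatment. All of this stands and limits the size that can be claimed.

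The generic comparisons in section 9.5.1 do not exclude an unadjusted comparison of episodes, and a fuller SAP is promised. This stands in part: section 9.5.4 still states the prior-count rule without condition and names no alternative.

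**Conclusion.** The point holds at minor to moderate severity. The secondary and exploratory labels conflict, and the only specified recurrent-event comparison between arms does not estimate the total randomised effect. At the planning-level rate the difference is at most about 1, 2 and 5 points at 3, 6 and 12 months, for v up to 1. At 3.06/year with uneven exposure it reaches 13 points at 12 months (58 v 45%, v = 1). With equal exposure and ×0.8 per episode it runs the other way (55 v 60%).

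A reader might infer that the planned model will understate efficacy, or that a gap of 10 points or more is to be expected. The documents support neither. They fix no frailty variance and no degree of acquired protection, so the direction cannot be known in advance. They also do not show that 3.06/year will apply in the trial, and the gaps at 3 and 6 months are smaller than at 12. The primary result, the first/only half of objective 4 and all decision rules are untouched.

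**What to change.** In the detailed SAP, before unblinding:
- State whether the all-episodes analysis is secondary or exploratory, and make objectives 4 to 6 and section 9.5.4 agree.
- Make the main all-episodes estimate an Andersen-Gill model with arm and the randomisation age group only and variance clustered on the child, or a negative binomial model with log person-time as offset.
- Keep the prior-count model as a sensitivity analysis, labelled as a conditional effect.

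This costs SAP wording and analysis code. It needs no new data or visits, and the sponsor's model is retained.

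A separate improvement, not part of the argument above, could be made in the same edit: include the randomisation age group in the time-to-first Cox model and log-rank test, and replace the rule that selects covariates by significant baseline difference with a fixed list (age group, enrolment time).

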9.5.5 Safety Analyses

Safety analysis will be primarily MITT where individuals who receive assignment but do not receive any product are excluded. Because of blinding and the brief length of time between assignment and administration, such cases will be very few. In the rare case of subjects receiving a regimen different from assignment, an as-treated analysis will be additionally performed where subjects will be analyzed according to the product they actually receive.

Safety data will be presented by line listings and tables at the individual level to provide details on safety events such as severity, duration, and relationship to study product. The number and percentage of subjects with 1 or more AE(s) will be summarized by dose arm along with the exact 95% confidence intervals of the AE rate. For subjects experiencing more than 1 AE, the subjects will be counted once under the event of highest severity.

In the efficacy study, comparisons between the dose arms and the control arm will be additionally performed in terms of the proportions of solicited AEs, related AEs, and SAEs.

In the rare case of subjects receiving a regimen different from assignment, a per-protocol analysis will be performed as a secondary analysis, which will include subjects according to the product they actually receive in the study.

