9 STATISTICAL CONSIDERATIONS

9.1 Statistical Hypothesis

The primary study hypotheses are that L9LS will be safe and will confer protection against Pf infection. In the dose-escalation study, the primary objective is to evaluate the safety and tolerability. In the efficacy study, the primary objective is to evaluate the efficacy of L9LS compared to placebo.

Primary Endpoints:

• Part 1 and Part 2: Incidence and severity of local and systemic AEs occurring within 7 days after the administration of L9LS, and incidence of SAEs throughout the study period.

• Part 2: Pf blood-stage infection as detected by microscopic examination of thick blood smear for 52 weeks after administration of L9LS or placebo.

Secondary Endpoints:

Data from both parts of the study will be used to assess the following endpoints:

- Pf blood-stage infection as detected by microscopic examination of thick blood smear for 12 and 24 weeks after administration of L9LS or placebo
- Pf blood-stage infection as detected by RT-PCR for 24 and 52 weeks after administration of L9LS or placebo.
- Incidence of clinical malaria (definition 1, see section 2.2.2.3) for 24 and 52 weeks after administration of L9LS or placebo.
- Incidence of clinical malaria (definition 2, see section 2.2.2.3) for 24 and 52 weeks after administration of L9LS or placebo.
- To assess the primary objective and first four secondary objectives among children 5-17 months of age.
- To assess the primary objective and first four secondary objectives among children 18-59 months of age.
- Measurement of L9LS in sera of recipients.
- PK analysis of L9LS and the association of L9LS concentration with Pf infection risk.
- PK analysis of L9LS and the association of L9LS concentration with clinical malaria risk.

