9.3 Sample Size Considerations for the Year 2 Extension Study

In part 1b of the study for evaluating the safety of L9LS at 30mg/kg and 40mg/kg, 12 new participants will be enrolled into each age-dose group where 9 participants will receive L9LS of 30mg/kg (or 40mg/kg) and 3 will receive placebo. The probabilities of observing 0 or more than 1 AE among the L9LS recipients within a group are presented in Table 5 over a range of possible true event rates.

In year 2 extension study, safety endpoints will be assessed within each arm, and each L9LS arm will additionally be compared with the placebo arm. Table 7 presents the minimum detectable difference in adverse event rate with 80% and 90% power over possible event rates under placebo, with each arm of 108 participants.

Table 7. The minimum detectable difference in event rate between L9LS arm and placebo arm

| Event rate | With 80% p | ower | With 90% power | | |
|------------|-------------------|------------|----------------|------------|--|
| (under | Detectable | Event rate | Detectable | Event rate | |
| placebo) | difference (under | | difference | (under | |
| | L9LS) | | | L9LS) | |
| 0.05 | 0.119 | 0.169 | 0.143 | 0.193 | |
| 0.1 | 0.143 | 0.243 | 0.17 | 0.27 | |
| 0.2 | 0.172 | 0.372 | 0.201 | 0.401 | |
| 0.3 | 0.186 | 0.486 | 0.215 | 0.515 | |

In year 2 extension study to assess the protective efficacy, each L9LS arm will be compared with the placebo arm. Assuming a lost to follow up rate of 20%, Table 8 shows the comparison power at various rates of the infection with 108 participants per arm. In addition, the two L9LS arms will also be compared with each other, and the comparison power is shown in Table 9.

Table 8.The comparison power with 108 participants per arm and a lost to follow up rate of 20%

| Sample | Lost to | Infection rate | Infection rate | mAb | Power |
|----------|-----------|-----------------|----------------|----------|-------|
| size per | follow up | (under placebo) | (under L9LS) | efficacy | (%) |
| arm | rate | | | | |
| | (%) | | | | |
| 108 | 20% | | 0.225 | 0.5 | 89 |
| | | 0.45 | 0.18 | 0.6 | 97 |
| | | | 0.135 | 0.7 | 100 |
| | | | 0.2 | 0.5 | 82 |
| | | 0.4 | 0.16 | 0.6 | 95 |
| | | | 0.12 | 0.7 | 99 |
| | | | 0.175 | 0.5 | 75 |
| | | 0.35 | 0.14 | 0.6 | 90 |
| | | | 0.105 | 0.7 | 98 |

Table 9. The comparison power between two L9LS arms with 108 participants per arm and a lost to follow up rate of 20%

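### No between-arm estimate or interval is planned for the L9LS-versus-placebo safety comparison; for uncommon events, a true doubling would usually be non-significant

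*Combined protocol and SAP*

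**What the plan says.** Section 9.1 puts safety first: "The primary study hypotheses are that L9LS will be safe and will confer protection against Pf infection". Section 1.1 states the first primary objective of the extension as safety and tolerability of the third and fourth doses compared with placebo. The part 2 safety objective names no comparator.

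Section 9.5.5 plans line listings, tables by severity and relationship, and AE counts and percentages that "will be summarized by dose arm along with the exact 95% confidence intervals of the AE rate". For part 2 it adds that "comparisons between the dose arms and the control arm will be additionally performed in terms of the proportions of solicited AEs", related AEs and SAEs. For the extension, Section 4.1.1 plans arm 1 versus 3, arm 2 versus 3, and arms 1 and 2 together versus 3. Section 9.3 sizes the single-arm contrasts: "Table 7 presents the minimum detectable difference in adverse event rate with 80% and 90% power over possible event rates under placebo".

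The method comes from the general rules in Section 9.5.1: "Formal comparisons will use standard methods, contingency tables for categorical variables", and "Unless specified in the subsequent sections, comparisons will be two-sided with type I error rate of 0.05". The intervals promised there belong to estimates tabulated by treatment arm: "This will include point estimates (mean, geometric mean, median, or proportions) and their respective 95% confidence intervals". Section 9.5.4 names a melded 95% interval for the between-arm efficacy estimate. No counterpart is named for safety.

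**The concern.** The comparison with placebo asks how large an excess of adverse events on L9LS remains compatible with the data. Two separate intervals, one per arm, do not answer that directly, and neither does a p-value. When events are few, a test at 0.05 can be non-significant while a sizeable excess is still possible. As written, the plan specifies a contrast with an interval for benefit and none for harm.

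The point bears most on SAEs and related AEs, two of the three categories to be compared. Section 2.3.1 reports no SAEs in part 1 or in the Mali paediatric L9LS trial. That makes low rates plausible, although part 1 followed children for only three months. If the tables show only per-arm rates and a p-value, a reader could take non-significance as reassurance that the data do not give.

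**Working it through.** **Inputs.** Two-sided alpha 0.05 (9.5.1); 108 per arm (9.3, Table 7); 216 L9LS versus 108 placebo when the L9LS groups are pooled (Table 1 and 4.1.1). The 20% loss used in Table 8 leaves 86 per arm (0.8 × 108 = 86.4). The documents give no placebo AE or SAE rate, so 2–30% is assumed.

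**Formula.** For n per arm, p̄ = (p₁ + p₂)/2, SE₀ = √[2p̄(1 − p̄)/n], SE₁ = √{[p₁(1 − p₁) + p₂(1 − p₂)]/n}, and power = Φ[(|p₂ − p₁| − 1.96·SE₀)/SE₁].

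**Reproducing Table 7.** For 5% versus 16.9%: p̄ = 0.1095, SE₀ = 0.0425, SE₁ = 0.0417, so (0.119 − 0.0833)/0.0417 = 0.856 and power = 0.804. The other stated differences give 0.800–0.804 for the 80% column and 0.901–0.902 for the 90% column. Table 7 is therefore the uncorrected pooled test at 108 per arm with no loss to follow-up. At a 5% placebo rate, 80% power needs a rise to 16.9%, which is 3.4-fold.

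**Power for a true doubling.** For 5% versus 10%: p̄ = 0.075, SE₀ = 0.0358, SE₁ = 0.0357, so (0.05 − 0.0702)/0.0357 = −0.57 and power = 0.285. The table uses the same method, with Fisher power from enumerating the binomial outcomes. For unequal arms, each SE uses its own arm sizes.

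| Placebo → L9LS | 108 v 108, pooled / Fisher | 216 v 108, pooled / Fisher | 86 v 86, pooled |
|---|---|---|---|
| 2% → 4% | 14% / 5% | 13% / 9% | 12% |
| 5% → 10% | 29% / 21% | 32% / 29% | 24% |
| 10% → 20% | 54% / 47% | 64% / 62% | 45% |
| 20% → 40% | 90% / 87% | 96% / 96% | 82% |
| 30% → 60% | 99.5% / 99% | >99% / >99% | 98% |

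Enumerating the uncorrected test at 108 v 108 instead of using the normal formula gives 12%, 29%, 55%, 90% and 99%.

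Power for a doubling crosses 50% at a placebo rate of about 9% (108 v 108). The crossing is at about 11% with a continuity correction or with 86 per arm, and about 8% at 216 v 108. Below roughly 8–11%, then, a doubling is missed more often than it is found.

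**What an interval would show (assumed counts).** For 10/108 versus 5/108, Fisher p = 0.28. The difference is 0.0926 − 0.0463 = 0.0463. Wilson limits are 0.0511 to 0.1621 and 0.0199 to 0.1038. The Newcombe limits are:

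- upper: 0.0463 + √[(0.1621 − 0.0926)² + (0.0463 − 0.0199)²] = 0.121
- lower: 0.0463 − √[(0.0926 − 0.0511)² + (0.1038 − 0.0463)²] = −0.025

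So the test is non-significant, while an excess of up to 12.1 points is not excluded. With equal counts, 5/108 versus 5/108, the limits are ±√[(0.1038 − 0.0463)² + (0.0463 − 0.0199)²] = ±6.3 points.

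**Expected precision when true rates are equal (Wald).** The half-width 1.96·√[2p(1 − p)/108] is 5.8 points at 5%, 8.0 at 10%, 10.7 at 20% and 12.2 at 30%. At 216 v 108 it is 5.0, 6.9, 9.2 and 10.6 points.

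**The case against.** Four counter-arguments have force.

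- **The power loss is not general.** A reader might infer that any doubling of adverse events would usually go undetected. The table does not support that. At two of Table 7's four placebo rates (20% and 30%) a doubling is detected with about 87–90% power or better at 108 per arm, and at 10% the chance is about even. If solicited AEs are common, the point has little force for them.
- **No rule reads non-significance as safety.** A reader might infer such a rule because safety is framed as a hypothesis. No section says so, and the part 2 safety objective has no comparator. Section 9.5.5 puts the descriptive summary first and the comparison second.
- **Safety does not rest on tests alone.** Per-arm exact intervals, listings, causality and severity assessment, pausing and halting rules (8.4.5, 8.4.6) and DSMB review of unblinded data (8.4.4.3.2) all inform it. For a rare serious event they are likely to act before any p-value.
- **The gap can be filled later.** Per-arm counts will be reported, so anyone can compute the difference. Section 9.5 also promises a detailed SAP, before unblinding, that supersedes the protocol.

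All four narrow the point; none supplies the missing contrast. Oversight rules govern conduct and do not estimate the excess over placebo. Nothing in the documents commits the later SAP to an interval.

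**Conclusion.** The point holds for the between-arm comparison of uncommon events. Sections 9.5.1 and 9.5.5 specify a two-sided 0.05 comparison with no effect estimate or interval, although the extension's first primary objective is explicitly relative to placebo and efficacy does get a between-arm interval. With an assumed placebo rate below roughly 8–11%, a true doubling would usually be non-significant: at 5%, power is 21–29% with 108 per arm and 29–32% with 216 versus 108.

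The size rests on assumed rates, because the documents give none, and on the unnamed choice of contingency-table test, hence the Fisher-to-chi-square ranges. The absence of an interval does not depend on those assumptions. This is a reporting change worth making. It does not show that the trial's safety assessment as a whole is inadequate.

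**What to change.** In Section 9.5.5 and the forthcoming SAP, for part 2 and the extension:

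- Report the risk difference, L9LS minus placebo, with a 95% confidence interval for solicited AEs within 7 days, related AEs and SAEs. Newcombe, Miettinen–Nurminen or the melded method would serve; name one.
- State the comparative result as the largest excess that the upper limit does not exclude.
- Add a sentence that a non-significant test will not be taken as evidence of safety.
- Optionally, put the expected upper limit for equal arms beside Table 7 (about +6 points at a 5% rate with 108 per arm).

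The cost is a few sentences and one column in the safety tables. Sample size, visits and conduct do not change, and no margin is needed. The downside is a less favourable-looking safety statement, since the upper limits for uncommon events will often be several percentage points.
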